Once the patient has given his signed consent, and patient is eligible to join the study, he will then be randomized into the experimental or control group using the online app https://www.random.org. The app generates a sequential list which prevents the investigator from learning allocation before a patient is registered into the study and from altering allocation afterwards, thus full concealment. Randomization will be performed by a research assistant not involved in the administration of treatments or data collection. The sequential list will be saved in a password protected file only accessible to the research assistant.. After a patient has been allocated, the group assignment will be permanent and unmodifiable. The randomization codes will be kept by the research assistant as well. Antibiotic or placebo will be administered by the stone center staff before the patient is put to sleep. The primary investigator will not be part of the biopsy procedure for blinding purposes.

Risks

One of the common side effects of prostate biopsy is infection. According to studies, 2% patients may experience mild disease not requiring hospitalization, and 1% may experience severe infections requiring hospitalization despite antibiotics. Based on literature, there will be no added risk of infection whether a patient is given antibiotics or not.

The most common side effect of antibiotic administration (Cefoxitin) is Diarrhea. Other rare side effects seen in less than 1% of patients given this drug includes Anemia, or decrease in hemoglobin, Increase in eosinophils in the blood, elevated liver enzymes, Decrease in platelets, and decrease in white blood cells. Patients who have allergies to antibiotics may also experience hypersensitivity reactions to this drug. There is also risk of alteration of the normal bacterial flora, which promotes antimicrobial resistance. This will decrease susceptibility of bacteria to antimicrobials making infections harder to treat.

Benefits

You will not receive direct benefits by participating in this study, however you may be spared from potential side effects of antibiotics. Furthermore, future prostate biopsy patients will benefit from enhanced guidelines on the need for prophylactic antibiotics to balance the risk of infection versus occurrence for antibiotic resistance.

Criteria for withdrawing subjects from the study and stopping the study as a whole

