Patients experiencing an adverse event such as symptoms of urinary tract infection like hematuria, dysuria, frequency, and urgency and systemic symptoms such as fever, generalized weakness, malaise will be evaluated right away initially with a complete blood count, urinalysis, and urine culture. Patients who will satisfy the criteria of Urinary Tract Infection, will be considered as having post biopsy infectious complications, and will be evaluated for possible sepsis. According to literature, 2% of patients undergoing prostate biopsy may experience mild post biopsy infection. 1% of patients may develop severe infections or urosepsis requiring hospitalization²². Computed sample size for the study is a total of 120 patients, with 60 patients in each arm. Hence, if more than 2 patients develop mild biopsy infection, and more than 1 patient develop severe infections from the experimental group, the study will be terminated and conclusion will be recommendation of administration of antibiotic prophylaxis. Patients who were not able to complete the procedure due to any circumstance, those who cannot tolerate anesthesia, those with adverse effects from anesthesia or antibiotics, and patients not compliant to follow up tests will be withdrawn from the study.

Data to be gathered

Patients who will pass the inclusion criteria will have their demographic data recorded such as age, sex, Height, Weight, BMI, Charlson Scores, Prostate volume, PSA, and History of Previous Biopsies. Post operatively, UTI will be assessed using a symptom checklist, which includes dysuria, urgency, frequency, or hematuria, fever, flank pain, nausea/vomiting. Signs of Systemic Inflammatory Response Syndrome (SIRS) will be gathered in patients who develop signs of urinary tract infection, namely, Temperature, Heart Rate, Respiratory Rate, White Blood Cell Count, and Blood Pressure. Incidence of sepsis and UTI In both groups will be recorded. Patients with Fever, or 2 or more signs of SIRS will be advised admission immediately. Histopathology results, 30 day readmissions, 30 day emergency room visit, and non infectious complications based on the Clavien Dindo classification will also be gathered.

Laboratory/assessment procedures to be performed

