A minimum sample of 60 patients per group is needed for a non-inferiority study with binary outcomes. Basourakos, et al reported that rates of post-biopsy genitourinary infections were 1.35% in the AP group and 1.22% in the NAP group²⁴. The target set was at least 80% power and 90% confidence interval. This was computed using Sealed Envelope Ltd. 2012. Power calculator for binary outcome non-inferiority trial. There are paucity of data regarding post prostate biopsy infections in patients without antibiotic prophylaxis. Similarly, data on post biopsy infections in Filipinos are lacking. A study reported by Yaddao, et al., published in the Philippine Journal of Urology, reported an infection rate of 5% occurring after biopsy, hence, we chose 5% as our non-inferiority limit.

Data Analysis

To assess the primary and secondary outcomes, we analyzed the 90% confidence interval (CI) of the difference in proportions, following Altman's recommendation. Non-inferiority was established if the upper bound of the 90% CI was less than 5%. Descriptive statistics, including median, percentages, 90% CI, or interquartile range (IQR), were reported as appropriate. For comparisons between groups, an independent t-test was used for continuous variables, while the chi-square or Fisher's exact test was applied for categorical variables. All statistical calculations were performed using MedCalc Statistical Software version 23.2.6

Ethical Considerations

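### 60 patients per group does not give 80% power at a 5% one-sided error: power is about 55% with a valid 90% interval, and the Wald interval that exceeds 80% doubles the type I error.

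*Protocol*

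**What the plan says.** The section Sample Size and Sampling Technique states that "A minimum sample of 60 patients per group is needed for a non-inferiority study with binary outcomes". It takes its planning rates from a published meta-analysis, in which "rates of post-biopsy genitourinary infections were 1.35% in the AP group and 1.22% in the NAP group" (AP is prophylaxis, NAP is none). It then says "The target set was at least 80% power and 90% confidence interval", and names as its tool an online "Power calculator for binary outcome non-inferiority trial". The limit comes from a local report of a 5% infection rate after biopsy: "hence, we chose 5% as our non-inferiority limit".

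The section Data Analysis gives the decision rule: "Non-inferiority was established if the upper bound of the 90% CI was less than 5" per cent. It refers to a recommended method for the interval of a difference in proportions but writes out no formula. The section on withdrawal and stopping repeats the size: "Computed sample size for the study is a total of 120 patients, with 60 patients in each arm".

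**The concern.** A sample size, a power, a confidence level, a limit and a decision rule are all fixed, so they can be checked against each other. The calculator relies on a normal approximation to the difference in proportions. With 60 patients per arm and rates near 1.3%, fewer than one infection is expected in each arm, and the approximation cannot be trusted there. The result turns on whether the no-prophylaxis arm has zero infections or one.

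If the analysis uses an interval that holds its level at such counts, a trial presented as having at least 80% power may be close to a coin toss on its own assumptions. If it uses the simple interval that matches the calculator, omission of prophylaxis may be declared non-inferior more often than the 90% level allows when it is truly 5 points worse. The trial is meant to inform guidelines on omitting prophylaxis, so either failure affects its main conclusion.

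**Working it through.** **Inputs (Protocol, sections Sample Size and Sampling Technique and Data Analysis).** n = 60 per arm; rate with prophylaxis (Group B) 1.35%; rate without (Group A) 1.22%; limit 5 points; 90% two-sided interval, so one-sided error 5% (z = 1.645); power 80% (z = 0.842). Expected infections: 60 × 0.0122 = 0.73 in A and 60 × 0.0135 = 0.81 in B.

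**1. Reproducing the 60.** The unpooled large-sample formula gives

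n = (1.645 + 0.842)² × (0.0135 × 0.9865 + 0.0122 × 0.9878) / (0.05 + 0.0135 − 0.0122)² = 6.183 × 0.02537 / 0.0513² = 59.6, rounded up to 60.

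The formula's own power at n = 60 is 80.2%. With equal rates it gives 60 at 1.22% and 66 (65.9) at 1.35%.

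**2. The decision at 60 v 60.** The rule is that the upper 90% limit for A minus B is below 5%.

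| Infections A v B | Newcombe upper limit | Wald upper limit |
|---|---|---|
| 0 v 0 | 4.3% (pass) | 0.0% (pass, zero width) |
| 1 v 0 | 7.1% (fail) | 4.4% (pass) |
| 1 v 1 | 5.6% (fail) | 3.8% (pass) |
| 1 v 2 | 4.2% (pass) | 3.0% (pass) |
| 2 v 3 | 5.3% (fail) | 4.3% (pass) |
| 2 v 4 | 3.9% (pass) | 3.2% (pass) |

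Newcombe, Agresti-Caffo, Farrington-Manning and Miettinen-Nurminen share one decision table: 0 in A always passes; 1 in A needs at least 2 in B; 2 needs at least 4; 3 needs at least 5.

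**3. Exact power at 1.22% v 1.35%.** Sum the binomial probabilities of the passing outcomes:

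- 0 in A: 0.9878^60 = 0.479.
- 1 in A and at least 2 in B: 0.355 × 0.194 = 0.069.
- 2 in A and at least 4 in B: about 0.001.
- Total: 0.549, so power is 54.9%.

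Wald also accepts 1 v 0 (probability 0.157), 1 v 1 (0.129) and 2 v 3, which brings its power to 84.0%.

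**4. Type I error at 60 v 60, with A exactly 5 points worse (6.35% v 1.35%).** The four small-count intervals give 3.7%; Wald gives 10.7% against the nominal 5%.

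**5. Is there a middle way?** Adding only the 1 v 1 outcome to the small-count table gives 67.8% power and already lifts type I error to 6.5%. A small change of method therefore does not reach 80% power at 5% error.

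**6. Sensitivity to the rates, equal in both arms, n = 60.** The 3% adds the two figures in the Risks section ("2% patients may experience mild disease not requiring hospitalization, and 1% may experience severe infections requiring hospitalization despite antibiotics"); the 5% is the local rate used to set the limit.

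| Rate in both arms | Power, small-count intervals | Power, Wald |
|---|---|---|
| 1.35% | 51% | 81% |
| 3% | 36% | 54% |
| 5% | 29% | 38% |

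**7. Size needed for 80%.** At 1.22% v 1.35%, exact power first reaches 80% at 99 per group with Newcombe (83.5%, type I error 4.9%) and at 100 with Miettinen-Nurminen (83.3%, 4.8%). Power moves in steps, so it is not smooth in n. These are evaluable patients, before any dropout.

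**The case against.** The strongest reply is that the protocol does not write out its interval. If the cited recommendation means the simple Wald interval, the stated power is met (84.0%) and the defect lies only in the error rate; the choice of interval could also be left to a statistical analysis plan. This narrows the power claim: 55% applies to the small-count intervals and not to every reading. It does not rescue the plan, because the protocol itself fixes size, power, confidence level, limit and rule, and no interval tried satisfies all of them at n = 60.

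Four smaller points stand:

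- The 60 is not a slip of calculation. It reproduces exactly, and the fault is the approximation behind it.
- The doubling of the Wald error belongs to the planning rates. At 8% v 3% it is 7.3%, and at 10% v 5% about 6.5%: inflated, but not doubled.
- The 3% and 5% rates are not the protocol's sample size assumptions. One is the sum of two figures in a risk statement and the other is the rationale for the limit, so they serve only as sensitivity values.
- The 60 depends little on an assumed advantage for omitting prophylaxis. Equal rates of 1.22% also give 60, and equal rates of 1.35% give 66.

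**Conclusion.** The concern holds. At the rates used to size the trial, 60 per group gives 54.9% power with an interval that keeps its level, or 84.0% power with a type I error of 10.7% where 5% is implied. The claim of at least 80% power with a 90% confidence interval is therefore wrong as written, whichever interval was meant.

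These figures assume exactly 60 evaluable patients in each arm, independent binomial counts, and true rates of 1.22% and 1.35%. If both rates are 1.35%, small-count power is 51%; at higher common rates it is lower still. The protocol withdraws some patients and states no dropout allowance. The effect of unequal or smaller arms was not quantified.

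**What to change.** In the section Sample Size and Sampling Technique, replace the claim of at least 80% power with the exact figure for the interval used: about 55% at 1.22% v 1.35%, and 51% if both rates are 1.35%. Power at 3% (36%) can be added, labelled as a sensitivity value.

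In the section Data Analysis, name one small-count interval for the decision (Newcombe or Miettinen-Nurminen) and rule out the simple Wald interval. Add the decision table for 60 v 60: 0 infections in Group A passes; 1 needs at least 2 in Group B; 2 needs at least 4; 3 needs at least 5. Say that it must be recalculated if the evaluable numbers differ. State that failing to meet the limit is inconclusive and is not in itself evidence that prophylaxis is needed.

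The cost is wording in two sections and a less favourable power statement, with no added patients. This makes the plan accurate but does not raise its power. If the sponsor wants to keep 80%, the alternative is about 99 to 100 evaluable patients per group: 198 to 200 in total against the present 120, before dropout.

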Prostate Cancer is the most common cancer among men. It is the 4th most common cancer worldwide. In 2020, 1.41 million people were diagnosed with prostate cancer ¹. Increased incidence is attributed to awareness and availability of resources to diagnose this disease. Prostate Specific Antigen (PSA) is the initial screening tool to diagnose prostate cancer, however. definitive diagnosis is achieved through tissue diagnosis through a biopsy². Historically, the transrectal approach has been the most common way to obtain prostatic tissue samples. Antibiotic prophylaxis is routinely given during the procedure, but despite this, 5-7% of patients develop post infectious complications. Infections requiring hospitalization are seen in 1-3% of patients³. Complications of prostate biopsy include bacteriuria, bacteremia, and sepsis⁴. Most infections are caused by bacterial transfer from the rectum to the prostate⁵ In recent years, Transperineal biopsies are being favored over transrectal biopsies for a number of reasons such as improved cancer detection rates, improved sampling of the anterior apex, and an overall reduced risk of false negative results. It is also considered as a sterile alternative to the standard Transrectal biopsy as it involves passing the needle through the perineal skin without having to pass through the rectum to reach the prostate ^{6,7}. Available literature showed a 2% rate of post infectious complications through this route⁶. A meta-analysis of eight observational studies suggests that the low infection rate after transperineal prostate biopsy is maintained without peri- procedural antibiotics. Presently, there has been no level 1 evidence to support this idea ⁵

V6 1/07/2025

According to the European Association of Urology guidelines on prostate biopsy, there is a growing evidence that antibiotics may be omitted in transperineal biopsies, however more clinical trials are required before making a final recommendation regarding this matter. This study aims to provide further evidence on surgical prophylaxis for transperineal prostate biopsies, and contribute to the growing concern of antimicrobial resistance⁸. This year alone, there has been no reported post procedure infectious complication following a transperineal biopsy. The question of whether antibiotics are indicated as prophylaxis remains unanswered.

Significance of the Project and Rationale:

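### The stated 80% power is a large-sample figure: at the protocol's own rates, 60 per arm gives about 55% exact power with any standard 90% interval that keeps its 5% error

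*Protocol*

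**What the plan says.** All the design inputs stand in the protocol.

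- **Size** (Sample Size and Sampling Technique): "A minimum sample of 60 patients per group is needed for a non-inferiority study with binary outcomes". The section on withdrawal and stopping repeats it: "Computed sample size for the study is a total of 120 patients, with 60 patients in each arm".
- **Rates** (Sample Size and Sampling Technique): "rates of post-biopsy genitourinary infections were 1.35% in the AP group and 1.22% in the NAP group". AP is prophylaxis (Group B) and NAP is no prophylaxis (Group A).
- **Targets:** "The target set was at least 80% power and 90% confidence interval".
- **Tool:** "This was computed using Sealed Envelope Ltd. 2012. Power calculator for binary outcome non-inferiority trial".
- **Margin:** "hence, we chose 5% as our non-inferiority limit".
- **Decision rule** (Data Analysis): "Non-inferiority was established if the upper bound of the 90% CI was less than 5" per cent.

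Data Analysis identifies the interval only by one author's recommendation and a software version. It gives no formula.

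**The concern.** A two-sided 90% interval compared with a margin implies a one-sided error of 5%. The protocol therefore promises two things of the same test: at least 80% power, and at most 5% risk of declaring non-inferiority when omission really adds 5 points of infection.

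With fewer than one infection expected in each arm, the result turns on whether Group A has 0, 1 or 2 events. A normal approximation can be far off there, and common intervals disagree about exactly those counts.

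Two things are at stake. Readers told of 80% power may take a failed trial as evidence against omitting prophylaxis, when failure was nearly as likely as success from the outset. And with one infection in Group A and none or one in Group B, the unstated choice of formula alone decides the conclusion.

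**Working it through.** **1. Reproduce the plan's figure.** Inputs: control rate 0.0135, experimental rate 0.0122, margin 0.05, one-sided alpha 0.05 (z = 1.645), power 0.80 (z = 0.842).

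n per arm = (1.645 + 0.842)² × [0.0135×0.9865 + 0.0122×0.9878] / (0.05 + 0.0013)² = 59.6, so 60. The approximate power at 60 is 80.2%. The sample size follows from the stated inputs.

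**2. Expected events.** 60 × 0.0122 = 0.73 in Group A and 60 × 0.0135 = 0.81 in Group B. The chance of no infections at all is 0.9878⁶⁰ = 47.9% in A and 0.9865⁶⁰ = 44.2% in B.

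**3. Which results pass.** Upper 90% bounds for A minus B with 60 per arm:

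| Infections A v B | Newcombe | Simple Wald |
|---|---|---|
| 0 v 0 | 4.31% pass | 0.0% pass |
| 1 v 0 | 7.13% fail | 4.39% pass |
| 1 v 1 | 5.62% fail | 3.84% pass |
| 1 v 2 | 4.23% pass | pass |
| 2 v 3 | 5.26% fail | pass |
| 2 v 4 | 3.90% pass | pass |

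Miettinen-Nurminen, Farrington-Manning, Agresti-Caffo and continuity-corrected Wald give the same decisions as Newcombe at these counts: A = 0 passes, A = 1 needs B of 2 or more, A = 2 needs B of 4 or more.

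**4. Exact power at 1.22% v 1.35%.** Sum the two binomials over the passing results.

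- *Error-controlling intervals:* P(A=0) + P(A=1)·P(B≥2) + P(A=2)·P(B≥4) = 0.4788 + 0.3548×0.1943 + 0.1293×0.0089 = 0.4788 + 0.0689 + 0.0011 = 0.549 (higher counts add less than 0.0001). With both arms at 1.35% the result is 51.4%.
- *Simple Wald:* P(A≤1) + P(A=2)·P(B≥3) = 0.8336 + 0.1293×0.0477 = 0.840.

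**5. False non-inferiority rate.** Same sums, with the true Group A rate equal to the control rate plus 5 points:

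| Control rate | Newcombe | Simple Wald |
|---|---|---|
| 0 | 4.6% | 19.2% |
| 1% | 3.6% | 12.2% |
| 1.35% (planning rate) | 3.7% | 10.7% |
| 2% | 3.8% | 8.8% |
| 5% | 4.6% | 6.5% |

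For control rates up to 10%, the Newcombe maximum is 4.9%.

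**6. Could another interval rescue the 80%?** Take rules that are monotone in the counts, which covers all the standard intervals. Accepting 1 v 0 costs 19.2% error at a zero control rate. Accepting 1 v 1 costs at least 5.5% at its worst control rate (6.7% if 0 v 0 also passes) and still yields only 67.8% power when added to the score-type pass region. Accepting 2 v 2 costs at least 7.3%. With these excluded, power at the planning rates cannot exceed 0.4788 + 0.3548×0.1943 + 0.1293×0.0477 + 0.0371×0.0089 = 55.4%.

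**The case against.** The strongest reply is that nothing was miscalculated. The protocol names its calculator, rates, margin and confidence level, and 60 per arm follows. That stands: this is not an arithmetic slip. But the target is stated as a property of the trial, and the test in Data Analysis does not have it.

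Second, the interval formula is commonly left to the SAP, which is not shown, and nothing in the protocol says that Wald will be used. A reader might infer that the trial will run at an inflated error rate; the documents do not support that. The point does not depend on it, because every standard choice leaves either the 80% or the 5% untrue.

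Third, a reader might pair 55% power with 19% error, citing the Introduction's remark that "there has been no reported post procedure infectious complication following a transperineal biopsy" this year. That reading fails. The 19.2% is the limit at a control rate of exactly 0, and score-type power is not short there: with equal arms it is about 75% at 0.5%, 89% at 0.2% and 100% at 0. The remark also gives no denominator and speaks only of reported cases. At other rates in the protocol the Wald excess is smaller: 8.8% at the 2% mild-infection figure and 6.5% at the 5% local figure behind the margin.

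Fourth, restating the power leaves a weak design in place. True: a stable 80% exact power would need about 91 (Agresti-Caffo) to 99 (Newcombe) per arm before dropout. An honest power statement is still owed at the size chosen.

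**Conclusion.** Wrong as written. At the protocol's own rates, 5% limit and 90% interval, 60 per arm gives about 55% exact power, not 80%, with any standard interval that keeps the one-sided error at or below 5% for control rates up to 10%. The shortfall is about 25 percentage points. The simple Wald interval restores the power (84%) at a false non-inferiority rate of about 11% at the planning control rate, roughly twice the implied 5%.

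The figures assume independent binomial counts, all 60 patients per arm analysed, and true rates of 1.22% and 1.35%. Power depends on these rates: a valid analysis fails in about 45% of trials at 1.22% v 1.35%, in about 49% at equal rates of 1.35%, and less often at lower rates. The 45% is therefore not a general failure rate under no excess risk.

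**What to change.** In Sample Size and Sampling Technique, keep the calculator result but label it a normal approximation, and state the exact power: about 55% at 1.22% v 1.35% and about 51% with both arms at 1.35%, for 60 per arm.

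In Data Analysis, name one error-controlling two-sided 90% interval for Group A minus Group B (Newcombe hybrid-score or Miettinen-Nurminen). State that the simple Wald interval will not be used, including when an arm has zero events. Settle this before event counts by arm are known.

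State that an upper bound of 5% or more means non-inferiority was not shown, which is not by itself evidence that prophylaxis is needed. Calling every such result inconclusive would go too far, since an interval lying wholly above 5% would show inferiority.

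Reconcile this wording, and any pass/fail table that is printed, with the section on withdrawal and stopping. That section ends the study on Group A counts (more than 2 mild and more than 1 severe infections) and attaches a conclusion recommending prophylaxis. The two passages must agree on what such counts lead to; which rule should apply is for the investigators.

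The cost is about a paragraph of wording and a less favourable stated power. No extra patients are required.

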The first comparative study on administering prophylaxis for transperineal biopsies was published in 2021 by Pirola et al. and they concluded that transperineal biopsies without prophylaxis was safe, and did not have a relevant impact on the incidence of post procedural infections, and that omission of pre operative antibiotics would critically reduce the unnecessary administration of antibiotics worldwide⁶.

Jacewisz et al. (2022) conducted a randomized controlled trial of patients who were suspected of having prostate cancer and were due to undergo transperineal prostate biopsies²¹. The patients were randomized into receiving prophylaxis or not. The non-inferiority threshold of 4% was not exceeded indicating that the rate of infections in patients who did not receive antibiotic prophylaxis prior to transperineal prostate biopsy was not higher than in those who did receive it. They concluded that it may be justifiable to exclude antibiotic prophylaxis in this particular population²¹.

A meta analysis and systematic review on infection rates after transperineal biopsy with and without prophylactic antibiotics was published in 2022 by Castellini, et al. included 8 studies involving 3,662 patients. A total of 2368 were given prophylaxis and 1294 patients were not. The review found that there were no significant differences in infection rate, fever, sepsis, or readmissions between patients with or without prophylaxis²².

In 2022, another systematic review was published of which included 106 studies, of which 37, 805 men received prophylaxis and 4772 men had none. Results showed that out of the group which received antibiotics, 19 developed sepsis. In the group without prophylaxis, only 4 developed sepsis. For overall infections, which includes non-septic infections, 403 out of 29,880 and 58 out of 4772 developed events. The results also showed no significant differences in the rates of infectious complications²³.

To date, there is still no definite guideline to whether antibiotic prophylaxis should be given or may be safely omitted for transperineal prostate biopsies despite growing body of evidence. More Randomized Clinical Trials are needed to reach this conclusion.

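### The 5-point non-inferiority limit is a total infection rate used as an allowable excess (4.7 times the planned control rate at the boundary), and it is the only limit given for primary and secondary outcomes

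*Protocol*

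**What the plan says.** Sample Size and Sampling Technique plans on a published review in which "rates of post-biopsy genitourinary infections were 1.35% in the AP group and 1.22% in the NAP group" (AP is with prophylaxis, NAP without). It adds that "The target set was at least 80% power and 90% confidence interval", and concludes that "A minimum sample of 60 patients per group is needed for a non-inferiority study with binary outcomes". The limit comes from a different source, a Philippine study that "reported an infection rate of 5% occurring after biopsy, hence, we chose 5% as our non-inferiority limit". No other argument for 5 points is given.

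Data Analysis then states: "To assess the primary and secondary outcomes, we analyzed the 90% confidence interval (CI) of the difference in proportions". The next sentence declares non-inferiority when the upper 90% bound is below 5%. It does not name the outcome or outcomes to which this applies, and no second limit appears.

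Description of Outcome Measures gives the primary outcome as urinary tract infection (UTI) and sepsis, without saying whether these form one composite or two endpoints. The secondary outcomes are 30-day admissions, 30-day emergency visits and non-infectious complications.

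On sepsis, the Background reports a review of 37,805 men with prophylaxis and 4,772 without: "out of the group which received antibiotics, 19 developed sepsis", against 4 in the group without. The section on withdrawal and stopping uses a broader figure of 1% for severe infection or urosepsis needing hospital care.

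**The concern.** A non-inferiority limit is the largest excess over control that one is prepared to accept. How often infection occurs in another series does not answer that question. Here the two numbers also pull against each other: the low rate (1.35%) sets the sample size and the high rate (5%) sets the limit. Each choice makes the trial smaller.

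The second problem is scope. An absolute limit of 5 points is wide for an outcome expected in about 1% of patients and nearly empty for one expected in well under 1%. With 60 per arm, a rare event will usually not occur at all, and the rule is then met whatever the relative risk. The protocol's summary says that the results are meant to help create international guidelines, so a statement of non-inferiority for sepsis or admission could carry weight that the data cannot give it.

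**Working it through.** **Inputs.** Sample Size section: 1.35% with and 1.22% without prophylaxis, limit 5 points, 80% power, 90% interval (one-sided 5%), 60 per arm. Background: sepsis 19/37,805 and 4/4,772. Withdrawal and stopping section: 1% severe infection or urosepsis. The 2% sepsis rate in step 5 is my assumption.

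**1. The stated sample size.** With the normal approximation,

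n per arm = (z₀.₉₅ + z₀.₈₀)² × [p₁(1−p₁) + p₀(1−p₀)] / [limit − (p₁ − p₀)]²

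Here (1.645 + 0.842)² = 6.183, the variance sum is 0.01205 + 0.01332 = 0.02537, and the denominator is (0.05 + 0.0013)² = 0.002632. The result is n = 59.6, so 60. The protocol's figure is reproduced.

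**2. The boundary.** 1.35% + 5 points = 6.35%, and 6.35/1.35 = 4.7.

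**3. If 5% were the control rate.** Same formula with 5% in both arms: 6.183 × 0.095 / 0.0025 = 234.9, so 235 per arm. Summing exact binomial probabilities at 60 per arm and 5% v 5%, the rule is met in 29% of trials with a Newcombe interval and 38% with a Wald interval.

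**4. Sepsis at the boundary, (rate + 5)/rate.**

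| Source in the protocol | Rate | Boundary / rate |
|---|---|---|
| Review, with prophylaxis, 19/37,805 | 0.050% | about 100 |
| Review, without prophylaxis, 4/4,772 | 0.084% | about 61 |
| Severe infection or urosepsis (broader) | 1% | 6 |

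**5. How often the 5% rule would be met for sepsis alone (60 per arm, exact enumeration).**

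| True rates, without v with prophylaxis | Newcombe | Wald |
|---|---|---|
| 0.05% v 0.05% | 97% | over 99.9% |
| 2% v 0.05% (assumed) | 30% | 66% |

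In the first row the expected count is 60 × 0.0005 = 0.03 cases per arm. The chance of no case at all among 120 men is (1 − 0.0005026)¹²⁰ = 94%, so the rule is nearly always met because nothing was observed. In the second row a 40-fold increase passes in roughly one third to two thirds of trials.

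**6. Infection, for comparison.** A true doubling, 2.7% v 1.35%, meets the rule in 26% (Newcombe) to 53% (Wald) of trials.

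**The case against.** **The sepsis verdict is not certain.** The planning rates and the source of the 5% are both infection rates. The post-biopsy infection definition in the Background includes urosepsis, and the rule sentence does not say that it is applied outcome by outcome. A single infection outcome is a fair reading, under which sepsis gets no verdict of its own. This stands: a reader might infer that sepsis is definitely tested against 5 points, and the text does not settle it. But the sentence before the rule names the secondary outcomes, and nothing confines the rule to one outcome.

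**The 100-fold figure uses the lowest rate.** That is so, and the range is 6 to about 100. The 0.05% is the only figure labelled as sepsis with prophylaxis, while the 1% covers a wider category, so each multiple needs its source beside it. The protocol also has a separate stopping criterion that includes severe infections in the no-prophylaxis group. It would not change the 30% and 66%, because passing trials in that scenario have essentially no more than one case in that group.

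**A boundary is not what usually passes.** Correct. At a true 6.35% v 1.35% the rule is met in only 3.7% (Newcombe) to 10.7% (Wald) of trials. The 4.7-fold figure describes the difference the protocol calls acceptable, not the typical result.

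**The earlier trial's 4% limit.** The Background says of that trial: "The non-inferiority threshold of 4% was not exceeded". A reader might infer that 60 per arm could never meet 4%, since 0/60 v 0/60 has a Newcombe upper bound of 4.3%. That does not follow: Newcombe gives 2.8% for 0 v 1, and Wald gives 0% for 0 v 0 and 3.8% for 1 v 1. Nor does another trial's 4% show by itself that 5% is an error.

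**Conclusion.** The point holds in two parts. First, the stated derivation of the limit is unsound: a total rate of 5% stands in for an acceptable excess, and against the protocol's own 1.35% the boundary is 6.35%, or 4.7 times control. If the 5% rate is taken seriously as the local control rate, the trial needs 235 per arm instead of 60. Second, 5% is the only limit in an analysis section that names primary and secondary outcomes, so the text allows a non-inferiority statement for rare events about which 60 per arm says almost nothing.

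The sample size of 60 is arithmetically right for its inputs. The sepsis figures apply only if sepsis is judged alone. The probabilities depend on the interval method, which the protocol identifies only by a reference to a published recommendation, so both Newcombe and Wald are shown.

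**What to change.** 1. State that the non-inferiority test applies to one composite only: any UTI or sepsis within 30 days.
2. Report sepsis, admissions, emergency visits and non-infectious complications as counts with exact or score-type intervals, and give no non-inferiority verdict for them.
3. Replace the derivation from the 5% rate with a plain statement that the limit is an accepted absolute excess of 5 points over an assumed 1.35%.
4. Limit the conclusion to: an excess of more than 5 points in the composite is excluded. Show the achieved upper bound, and make no safety claim for sepsis.

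The cost is wording and a narrower claim, with no patients added to the protocol's own calculation. This does not shrink the 4.7-fold boundary; it makes it visible. If a tighter limit were preferred, the same formula at 1.22% v 1.35% gives 92 per arm for 4 points and 346 per arm for 2 points.
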